Preliminary evidence of efficacy: Although severe acute post-operative pain is not the only risk factor for chronic post-surgical pain (CPSP), an intervention that does not decrease postoperative pain is unlikely to have a significant impact on CPSP. If the 80%

confidence interval for the between-group difference in average pain score in the 24-hour postoperative period favours LA block, we will consider that preliminary evidence of efficacy.^{65,66}

Secondary outcomes of the pilot trial include adverse events related to study interventions. We will also collect the outcomes for the definitive trial to test and refine data collection processes.

The primary outcome in the definitive trial is chronic pain, defined by the Pain Burden Index, measured at 3 and 6 months following surgery. The Pain burden Index examines postsurgical pain in four postoperative body areas. The Index is calculated as a sum of the four locations (breast, chest, axilla, arm) multiplied by the frequency of pain¹² (see Form 8: Pain Burden Index).

Secondary outcomes of the definitive trial include:

- Opioid analgesia requirements during surgery and in the first 24 hours after surgery, defined as morphine milligram equivalents (MME). The total MME will include intraoperative opioids administered in the OR and postoperative opioids administered/ingested in the Postanesthetic Care Unit (PACU), Surgical Day Care Unit (SDC), Inpatient Unit, and home in the 24-hour period after completion of surgery. Opioids consumed will be converted to MME (see Appendix 3: Calculation of Morphine Milligram Equivalents (MME)).
- Acute patient-reported pain scores:
 - Numerical Rating Scale (NRS; 11-point scale) measured at the standard time points of nursing care assessments: preoperatively (baseline); four times per hour in PACU until discharge; if admitted, hourly for 2 hours, and then every 6 hours in the Inpatient Unit; and at discharge from hospital; 24 hours after surgery is complete.
- Opioid-induced side effects:
 - Postoperative nausea and vomiting
 - Nausea severity (by Verbal Rating Scale) in PACU
 - Vomiting episodes (0-48 hours after surgery) in PACU & home
- Quality of recovery (Form 7: Quality of Recovery-15 Questionnaire)

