 - Measured with the Quality of Recovery-15 (QoR-15) scores at baseline prior to surgery and 24 hours after surgery⁶⁷⁻⁶⁹. This 15-item questionnaire assesses patient-reported pain, physical comfort, physical independence, psychological support, and emotional state.⁶⁹ It takes an average of 2.5 minutes to complete. The QoR-15 has been statistically validated and is designed for both ambulatory and inpatient surgery populations.^{68,70}
- Length of stay (LOS) in hours in hospital

- Measured from the time admitted to PACU to the time discharged from hospital. LOS includes time in the PACU, Surgical Day Care (SDC) and, if required, Inpatient Unit. Patients are transferred between units and discharged from hospital according to standardized institutional criteria (see Appendix 4: PACU and SDC Discharge criteria).
- Time-based outcome measures:
 - time to perform ultrasound-guided TPVB+
 - time under general anesthesia
 - time in PACU
 - failure of discharge from PACU and requiring admission
- Rescue medications:
 - Need for rescue opioid analgesics and anti-emetics
 - Rescue medications are defined as those required “as needed” (ie, beyond scheduled) in the PACU, ward, and after discharge
 - Time to rescue opioid analgesics and anti-emetics
- Failure of early discharge:
 - Emergency room visits within 48 hours of discharge
- Complications and adverse events
 - Related to the ultrasound-guided regional block: vascular or nerve injury, Horner’s syndrome, bleeding/hematoma, local anesthetic systemic toxicity, pneumothorax, distortion tissue planes during axillary dissection, and other.
 - Related to the surgery: hematoma, tissue necrosis, urgent unplanned return to the operative theater within 24 hours of surgery.

These measures are listed in Form 6: Clinical Form and Form 11: Data Collection Form.

Sample Size

240 IBR procedures are performed annually at MSJH, 50% participation yields ~ 30 patients in 3 months. Assuming a difference of 1 and standard deviation of 1.2, this sample size yields > 80% probability that the lower bound will exclude 0.⁴⁵

Additional Details of Study Design

Participants will also be given at the time of consent a post operative package. This will contain the Quality of Recovery-15 Questionnaire (Form 7), Recovery Booklet (Form 5) and Pain Burden Index (Form 8).

The Quality of Recovery-15 Questionnaire (see Form 7) is to be completed at 24 hours after surgery in paper format or electronic format (based on their preference). This

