24 hour time point will be marked on the QoR-15 form. If paper format is preferred, the QoR-15 will be provided with a paid-postage envelope to return once completed at 24 hours after surgery. The pain NRS at 24 hours will be recorded from the chart. The envelopes will be addressed to the research coordinator at UBC Hospital office. If the participant prefers electronic format, the questionnaire will be sent to their provided email address using secure online format (REDCap developed questionnaire).

Recovery Booklet (see Form 5) will include: a) schedule for taking prescription pain medications; b) a postoperative 7-day symptom diary (for recording pain on NRS at 24 hours, episodes of vomiting, nausea, and use of prescribed medications). Patients will be provided with a paid-postage envelope to return their Recovery Booklet via mail once completed at 7 days after surgery. Patients will be reminded to complete the Recovery Booklet (Form 5) in 3-4 days and once again at 14 days to return the envelope.

The Pain Burden Index questionnaire (see Form 8) asks specifically about pain in four surgically related body areas and to calculate the Pain Burden Index (PBI). The PBI is calculated by summing the pain severity scale (0–10) at each of four locations (breast, axilla, chest wall, arm) multiplied by the frequency of the pain at each site. The PBI questionnaire will be sent to participants via mail as paper format (with paid-postage envelope to return once completed) or email as electronic format (as per their requested preference) to be completed 3 and 6 months after their surgery. Details of present adjuvant treatments (radiation and chemotherapy) will also be included in the questionnaire.

Secondary outcomes data including opioid consumption and side effects, length of stay in hospital (hours), rescue medications, failure of early discharge, complications and adverse events and time-based outcome measures (time in PACU, time under general anesthesia, time to perform ultrasound-guided TPVB+, failure of discharge from PACU and requiring admission) will be collected through participants' charts and EMR.

Risk/Benefit Estimates [\(back\)](#)

Anticipated Benefits to Participants

Participants will be randomly assigned to receive TPVB+ nerve blocks with either local anesthetic or sham (saline) followed by general anesthesia.

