Participants will be randomly assigned to receive TPVB+ with local anesthetic or sham before general anesthesia. For all participants, data will be collected on the Intake Form, Clinical Form, Quality of Recovery-15 Questionnaire, Pain Burden Index, and Recovery Booklet in the following 7 sections:

1. The Intake Form will be completed by the patient during the initial contact phone call and includes information on general demographics and inclusion/exclusion criteria (without identifying information).
2. The first section of the Clinical Form will be used to record information on the perioperative course including the type of surgery performed: unilateral or bilateral; partial or total mastectomy with or without sentinel lymph node biopsy or axillary lymph node dissection; tissue expander or immediate implant reconstruction; adjunctive procedures will be recorded including biopsies and balancing reduction procedures.
3. The second section of the Clinical Form will record information on the general anesthesia provided; preoperative medications, intraoperative analgesics, sedatives, antiemetics, and anxiolytics. The form will also include details on the regional block and time to perform the block. Surgical and regional block complications within 24 hours of surgery will be recorded.
4. The third section of the Clinical Form will include information on participant-reported pain scores and medications in the postanesthetic care unit and inpatient ward.

5. The Quality of Recovery-15 Questionnaire will be completed by the participant at baseline before surgery and at 24 hours after surgery to evaluate the quality of their recovery.
6. The Recovery Booklet will be completed by the participant during the first 7 days after surgery to track scheduled and rescue medications required, opioid-related side effects (nausea and vomiting), and pain at 24 hours after surgery.
7. The Pain Burden Index will be completed by the participant 3 months and 6 months after surgery to evaluate for the presence and severity of chronic pain.

Confidentiality [\(back\)](#)

Management of Identifying Data:

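### The 0-48 hour vomiting outcome counts only PACU and home, so as defined it leaves out Surgical Day Care and the Inpatient Unit

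*Protocol*

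**What the plan says.** The Outcome Measures section lists opioid-induced side effects among the secondary outcomes of the definitive trial. One of them is "Vomiting episodes (0-48 hours after surgery) in PACU & home". The pilot also collects these outcomes, to try out and improve data collection.

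Other outcomes in the same section cover more of the hospital:

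- Opioid use in morphine equivalents: postoperative opioids are counted in the "Postanesthetic Care Unit (PACU), Surgical Day Care Unit (SDC), Inpatient Unit, and home".
- Length of stay: "LOS includes time in the PACU, Surgical Day Care (SDC) and, if required, Inpatient Unit".
- Rescue opioids and anti-emetics: as-needed drugs "in the PACU, ward, and after discharge".

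Three places describe where vomiting data come from:

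- Additional Details of Study Design says that the Recovery Booklet contains "a postoperative 7-day symptom diary (for recording pain on NRS at 24 hours, episodes of vomiting, nausea, and use of prescribed medications").
- The same section opens its list of chart and EMR data with "Secondary outcomes data including opioid consumption and side effects", and excludes no unit.
- Data Collection, item 4, says that the third section of the Clinical Form holds "information on participant-reported pain scores and medications in the postanesthetic care unit and inpatient ward". Item 6 says that the Recovery Booklet tracks nausea and vomiting over the first 7 days.

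**The concern.** A count over 0-48 hours should cover wherever the patient is during those hours. Taken literally, the definition stops counting when the patient leaves PACU and starts again at home. A same-day patient has a gap for the SDC stay. An admitted patient has a gap for the whole ward stay.

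The gap is not independent of the outcome. Uncontrolled vomiting is a reason to be kept in SDC, which is one of the places where the definition does not count. The Hypothesis section expects the block to reduce both nausea and vomiting and length of stay. If it does, sham patients would spend more of the window in uncounted places, and the outcome would understate the benefit it is meant to measure. A definition carried unchanged from the pilot into the definitive trial would carry this with it.

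**Working it through.** The protocol states no figure for this outcome, so there is none to reproduce. The check sets the relevant places side by side and then works out the direction of any bias.

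**Step 1: locations named, by outcome (Outcome Measures).**

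| Outcome | PACU | SDC | Inpatient Unit / ward | Home / after discharge |
|---|---|---|---|---|
| Opioid use | yes | yes | yes | yes |
| Length of stay | yes | yes | yes, if required | not applicable |
| Rescue opioids and anti-emetics | yes | not named | yes | yes |
| Vomiting, 0-48 h | yes | **not named** | **not named** | yes |

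One result is that a rescue anti-emetic given on the ward counts toward its outcome, while the vomiting that prompted it falls outside the vomiting outcome.

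**Step 2: is the omitted time related to vomiting?** The SDC Discharge Score (Appendix 4) has a nausea/vomiting category. Uncontrolled symptoms score 0, and a 0 in any category bars discharge. Symptoms controlled with medication score 1 and do not bar discharge by themselves. The link therefore runs through uncontrolled symptoms in SDC. The PACU criteria in the same appendix mention nausea only. A patient held back by them stays in PACU, where vomiting is counted, so they do not support the point.

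**Step 3: direction of the bias.** Let m be the true mean number of episodes in 0-48 hours and f the share of them that occurs in SDC or on the ward, with S for sham and L for local anesthetic. Under the literal definition:

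- Counted difference = m_S(1 − f_S) − m_L(1 − f_L) = (m_S − m_L) − (m_S f_S − m_L f_L).
- If m_S > m_L, f_S ≥ f_L and f_S > 0, then m_S f_S > m_L f_L. The counted difference is then smaller than the true one.
- If f_S = f_L, the ratio of means is unchanged and only the absolute difference shrinks. If f_S > f_L, the ratio also moves toward 1.
- A reversed sign needs (1 − f_S)/(1 − f_L) < m_L/m_S.

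The protocol gives none of m_S, m_L, f_S or f_L, nor an SDC time or admission rate from which to approximate them. The direction follows from the stated conditions. The size does not.

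**Step 4: do the data sources fill the gap?** They may, but the protocol does not settle it.

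- The diary covers 7 postoperative days, is not limited to home, and is handed over at consent, so the patient has it in hospital.
- Additional Details of Study Design has the booklet mailed back once completed at 7 days. The Confidentiality section (Management of Non-Identifying Data) has the same 7-day booklet completed before the patient leaves hospital. For same-day or next-day discharge these do not fit together.
- The first stated reminder to fill in the booklet comes at 3-4 days, after the 48-hour window has closed.
- Charts and EMR are a source for side effects in any unit, but the Clinical Form summary for PACU and ward names pain scores and medications only.

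Even where a source records an SDC or ward episode, someone applying the outcome definition as written would leave it out.

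**The case against.** The strongest reply is that this is loose wording and no data are missing. PACU and home may be shorthand for before and after discharge, and the parent bullet on postoperative nausea and vomiting sets no location limit. The diary and the chart review can both record vomiting in SDC or on the ward. The Outcome Measures section also says that its measures are listed in Forms 6 and 11, and Forms 5, 6 and 11 are not shown, so a vomiting field for the ward may already exist.

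Most of this stands. A reader might infer that SDC and ward episodes are lost. The documents do not support that: the episodes fall outside the stated definition, but nothing shows that they go unrecorded. The one-line summary of the Clinical Form cannot establish that the form lacks a field.

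A reader might also try to put a size on the gap. A hospital stay of 18 to 24 hours after PACU would take up 18/48 = 37.5% to 24/48 = 50% of the window. That stay is an assumption with no source in the protocol, and a share of hours is not a share of episodes. A claim that the comparison could reverse has no input behind it either. The earliest episodes, those in PACU, are counted in any case.

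The reply does not remove the gap in the definition. The opioid outcome in the same list names each unit separately, so a reader has good reason to take the shorter list for vomiting at its word.

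**Conclusion.** The point holds as a defect of definition. As written, the outcome excludes SDC and Inpatient Unit time inside its own 0-48 hour window, and through the SDC discharge score the excluded time is related to vomiting. If the block reduces vomiting, if sham patients have at least as large a share of their episodes in those units, and if the definition is applied literally, the comparison is biased toward no difference. The amount cannot be estimated from the protocol.

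The consequence is minor. Vomiting is one of many secondary outcomes of the definitive trial. The pilot's three feasibility criteria (enrolment, block success and 6-month retention) do not use it, and neither does the 80% confidence interval rule for the 24-hour pain score.

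**What to change.** - In Outcome Measures, define the outcome as the number of vomiting episodes from 0 to 48 hours after surgery in all locations: PACU, SDC, Inpatient Unit and home.
- State that chart/EMR and the diary are the sources for hospital time after PACU.
- Check that Form 6 has a vomiting field for SDC and for the ward, and add one if it does not.
- Reconcile Additional Details of Study Design, Data Collection (items 4 and 6) and Management of Non-Identifying Data on when and where the Recovery Booklet is completed.

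The cost is a line or two of text, possibly one form field, and slightly more chart abstraction. It changes measurement only and leaves patient care as it is. It also fits the pilot's stated purpose of refining data collection before the definitive trial.

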Identifying information collected from potential participants includes: name, phone number/email (optional, only if provided by participant), age/date of birth, PHN, and mailing address. This identifying information will be stored in the Code Break. All potential participants will be assigned a Recruitment ID number (i.e. R01). The identifying information from potential participants who opt not to participate in this study will be deleted from the Code Break. After consent is obtained, each participant will be assigned a study number (i.e. NB01). This study ID number will be recorded in the Code Break. Identifying information will only be stored in the Code Break, with the exception of email on REDCap as outlined below.

The Code Break will be password-protected and stored on a secured UBC server. Email for the patients who opted for emailed surveys will be entered into REDCap.

The Consent Form will be stored in a locked secured filing cabinet in the Principal Investigator's (PI's) Office.

Management of Non-Identifying Data:

All non-identifying information collected will be kept on the completed Recruitment Log, Study Data Log, Intake Form, Clinical Form, Quality of Recovery-15 Questionnaire, Recovery Booklet, and Pain Burden Index as hard copies in a locked secured filing cabinet in the Principal Investigator's (PI's) office.

The Recruitment Log will record Recruitment ID number and consent progress. The Study Data Log containing tasks for research staff will be associated with Study ID number. The Recruitment Log and Study Data Log will not contain any identifying information.

The hard-copy Intake Form and the Baseline Quality of Recovery-15 (QoR-15) Questionnaire (Form 4) will be collected at the time of enrollment. An additional Quality of Recovery-15 (QoR-15) Questionnaire (Form 7) will be provided on the day of surgery to be completed 24 hours postoperatively, before discharge from hospital and then mailed

back. Both the Intake Form and the Quality of Recovery-15 (QoR-15) Questionnaires will be stored with the other hard-copy study forms in a locked secured filing cabinet in the PI's office.

The hard-copy Recovery Booklet (Form 5) will be given to participants and completed over the course of 7 days postoperatively, before discharge from hospital. The Recovery Booklet will be stored with the other hard-copy study forms in a locked secured filing cabinet in the PI's office.

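### The only stated Recovery Booklet reminders come after the 24-hour opioid and 48-hour vomiting windows have closed, and the protocol contradicts itself on where and from what source post-discharge data are recorded

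*Protocol*

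**What the plan says.** Under Outcome Measures, the opioid total includes doses taken at "home in the 24-hour period after completion of surgery". The side-effect outcome is "Vomiting episodes (0-48 hours after surgery) in PACU & home". Both windows therefore extend past discharge for a patient who goes home early.

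Under Additional Details of Study Design, the Recovery Booklet (Form 5) contains "a postoperative 7-day symptom diary (for recording pain on NRS at 24 hours, episodes of vomiting, nausea, and use of prescribed medications". It is part of a package handed out at consent. Patients are to "return their Recovery Booklet via mail once completed at 7 days after surgery". The reminder plan is: "Patients will be reminded to complete the Recovery Booklet (Form 5) in 3-4 days and once again at 14 days to return the envelope". The same section says that opioid use, side effects and rescue medications come from charts and the EMR, and that the 24-hour pain score comes from the chart.

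Under Data Collection: "The Recovery Booklet will be completed by the participant during the first 7 days after surgery to track scheduled and rescue medications required". That item also lists nausea, vomiting and pain at 24 hours.

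Under Confidentiality, Management of Non-Identifying Data, the booklet is to be "completed over the course of 7 days postoperatively, before discharge from hospital", and the follow-up QoR-15 (Form 7) is "to be completed 24 hours postoperatively, before discharge from hospital and then mailed" back.

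**The concern.** A patient at home has only one described form for tablets taken and vomiting after discharge, the booklet. The first prompt to fill it in comes once the period of interest is over. A patient who has not started by then can only reconstruct the first two days from memory or leave them blank.

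The instructions also disagree on where and from what source these data are obtained. Staff who followed the Confidentiality wording literally would expect the booklet and the 24-hour QoR-15 to be finished in hospital, and home data would be lost. Staff who followed the statement on charts and EMR would look for home doses and vomiting where they would not ordinarily be found.

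The pilot collects the definitive trial's outcomes in order to test and refine data collection, so this procedure is itself part of what is being tried out.

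**Working it through.** The protocol gives no figure for this point, so there is nothing to reproduce. The check compares times and then compares sections.

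**Timing.** Inputs: first reminder at 3 to 4 days (Additional Details of Study Design); opioid window closing at 24 h and vomiting window closing at 48 h (Outcome Measures). The protocol does not say from when the 3 to 4 days run; counting from surgery is assumed.

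- Reminder time: 3 × 24 = 72 h to 4 × 24 = 96 h.
- Delay after the opioid window: 72 − 24 = 48 h to 96 − 24 = 72 h.
- Delay after the vomiting window: 72 − 48 = 24 h to 96 − 48 = 48 h.

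If the days were counted from discharge, the delays would be longer. The reminder falls about midway through the 7-day diary. The day-14 reminder concerns return of the envelope.

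**Is there an earlier prompt?** The call on the day before surgery (Recruitment) covers the intake form, baseline QoR-15 and consent form, not the booklet. The Pain Burden Index, by contrast, is sent one week before each due date with a phone call (Confidentiality). The text describes no such advance prompt for the 24-hour and 48-hour entries.

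**Sections side by side.**

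| Item | One statement | Conflicting statement |
|---|---|---|
| 7-day booklet | Mailed back once completed at day 7 (Additional Details) | Completed before discharge (Confidentiality) |
| 24-hour QoR-15 | Paper form mailed, or electronic form sent by email (Additional Details) | Completed before discharge, then mailed (Confidentiality) |
| Opioids and vomiting after discharge | Booklet tracks medications, nausea and vomiting (Data Collection) | Charts and EMR (Additional Details) |
| 24-hour pain score | Chart (Additional Details) | Booklet (Additional Details and Data Collection) |

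The length-of-stay definition routes patients through PACU and Surgical Day Care, with the inpatient unit only if required. A 7-day diary cannot be finished in hospital on that pathway. A patient already home at 24 hours can have a charted score at that time only if someone contacts her, and no such contact is described.

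**Number of patients.** The Sample Size section gives 240 procedures a year and 50% participation over 3 months: 240 × 0.5 × 3/12 = 30. Two added contacts each: 2 × 30 = 60.

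**The case against.** The booklet is a diary handed out before surgery and meant to be filled in as events happen. It also holds the medication schedule, and Appendix 2 refers to it for discharge prescriptions, so patients have reason to open it from the first doses. On that view the day 3-4 message is a mid-diary adherence prompt, not the start of recording. This stands. A reader might infer that home data will be recalled or missing, but the documents give no completion rate and support only that early entries are unprompted.

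The day 3-4 reminder concerns the booklet alone. The QoR-15 has its 24-hour point marked on it, and the electronic version arrives by email, though no send time is given. This also stands: the reminder timing is no criticism of the QoR-15, which is affected only by the pre-discharge wording.

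Forms 5, 11 and 12 and the Appendix 5 diagram are not visible, and one of them could carry an earlier contact. This stands as a limit, so the finding is about what the text states. It would not remove the contradictions between sections.

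Finally, these are secondary data in a small pilot, and no feasibility criterion uses them. That is correct and limits the weight of the point. The 24-hour pain score may feed the average used for preliminary efficacy, but how that average is built is not stated.

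**Conclusion.** The point holds as an inexpensive improvement together with a contradiction that needs reconciling. Counted from surgery, the first stated booklet prompt comes 48 to 72 hours after the opioid window closes and 24 to 48 hours after the vomiting window closes. Entries for those periods made at home are unprompted and may be late, recalled or missing in some patients. The pre-discharge wording for Forms 5 and 7 cannot be squared with mail-back and home outcomes, and the source statements conflict for post-discharge opioids, vomiting and the 24-hour pain score. Sample size and feasibility criteria are unaffected.

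Two stronger readings should be resisted. A reader might take the discharge prescription's range of one to two tablets per dose as showing a twofold error in the opioid count. It only restates what is prescribed, says nothing about recall error, and covers just part of a total that also includes intraoperative and in-hospital opioids. A reader might also infer that data quality will differ by arm because the block may shorten stay. The protocol gives no same-day discharge rate for either arm, so that is conjecture.

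The verdict assumes that the 3 to 4 days run from surgery, that no unseen form schedules an earlier contact, and that charts do not ordinarily record events at home.

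**What to change.** 1. Under Additional Details of Study Design, add a short call or REDCap message from the existing research assistant at 24 hours (booklet entries, 24-hour pain score and QoR-15) and another at 48 hours (vomiting). Keep the day 3-4 and day-14 reminders, since the first still supports the later diary days. State that all times run from the end of surgery.
2. Record the date and time at which each 24-hour item was completed, so that late entries can be identified. No rule setting late forms to missing is needed here: it could remove mostly the patients already at home, and such windows are commonly left to the SAP.
3. Under Confidentiality, delete the requirement to complete Forms 5 and 7 before discharge.
4. Under Additional Details of Study Design, name the booklet as the source for opioid use, vomiting and the 24-hour pain score after discharge, and the chart as the source while the patient is in hospital.

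Cost: about 60 brief contacts over the pilot, some at weekends, and wording changes in two sections. No treatment or sample size changes.
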